2. OBJECTIVES/ENDPOINTS

Objectives	Endpoints				
Pri	mary				
To evaluate the humoral immune response following a 1-dose primary schedule of RSVPreF3 OA investigational vaccine up to 12 months post-Dose 1.	 Humoral immune response at pre-vaccination (Day 1), 30 days post-Dose 1 (Day 31), and at 6 and 12 months post-Dose 1 (Months 6 and 12), in a subset of participants: Neutralizing antibody titers against RSV-A Neutralizing antibody titers against RSV-B. 				
Sec	ondary				
To further evaluate the humoral immune response following a 1-dose primary schedule of RSVPreF3 OA investigational vaccine up to 12 months post-Dose 1.	 Humoral immune response at pre-vaccination (Day 1), 30 days post-Dose 1 (Day 31), and at 6 and 12 months post-Dose 1 (Months 6 and 12), in a subset of participants: RSVPreF3-specific Immunoglobulin G (IgG) antibody concentrations. 				
To evaluate the humoral immune response following 1 dose of the RSVPreF3 OA investigational vaccine and following revaccination doses, up to study end.	 Humoral immune response at Months 18, 24, 30 and 36 post-Dose 1, and at 1 month after each revaccination dose (Months 13 and 25), in a subset of participants: Neutralizing antibody titers against RSV-A and RSV-B RSVPreF3-specific IgG antibody concentrations. 				
To evaluate the cell-mediated immune (CMI) response following 1 dose of the RSVPreF3 OA investigational vaccine and following revaccination doses up to study end.	 CMI response at pre-vaccination (Day 1), 30 days post-Dose 1 (Day 31), at Months 6, 12, 18, 24, 30 and 36 post-Dose 1, and at 1 month after each revaccination dose (Months 13 and 25), in a subset of participants: Frequency of RSVPreF3-specific CD4+ and/or CD8+ T cells expressing at least 2 activation markers including at least one cytokine among CD40L, 4-1BB, IL-2, TNF-α, IFN-γ, IL-13, IL-17. 				
To evaluate the safety and reactogenicity of each vaccination schedule of the RSVPreF3 OA investigational vaccine in all participants.	 Occurrence of each solicited administration-site and systemic event during a 4-day follow-up period (i.e., on the day of vaccination and 3 subsequent days) after each vaccination. Occurrence of any unsolicited AE during a 30-day follow up period (i.e., on the day of vaccination and 29 subsequent days) after each vaccination. Occurrence of all SAEs and pIMDs up to 6 months after each vaccination. Occurrence of fatal SAEs, related SAEs and related pIMDs from first vaccination (Day 1) up to study end (Month 36). 				
Tertiary					
To further characterize immune responses to the RSVPreF3 OA investigational vaccine.	 Any further exploratory immunology in a subset of participants, such as, but not limited to: Antibodies against specific protein F epitopes. Potential new immunological markers for protection. Frequency of RSVPreF3-specific CD4+ and/or CD8+ T cells expressing one or any combination of immune marker(s) 				

CMI = cell-mediated immunity, AE = adverse event, SAE = serious adverse event, pIMD = potential immune-mediated disease.

3. STUDY DESIGN

3.1. Overall design

Figure 1 Study design overview

N = number of participants; D = day; M = month; AE = adverse event; HI = humoral immunity; CMI = cell-mediated immunity; pIMD = potential immune-mediated disease; SAE = serious adverse event.

= blood sample for humoral immune responses (only applicable for ~ 345 participants of the RSV_annual group; and for all participants of the RSV_flexible revaccination and RSV_1dose groups)

I = blood sample for CMI (only applicable for ~345 participants of the RSV_annual group, and for ~115 participants each from the RSV_flexible revaccination and RSV_1dose groups).

Note: For group RSV_annual: Revaccination Year 1 = Month 12; Revaccination Year 2 = Month 24; for group RSV_flexible revaccination: Revaccination Year 2 = Month 24.

*Visit and follow-up of solicited events, unsolicited AEs, SAEs and pIMDs are only applicable for RSV_annual group. **Visit and follow-up of solicited events, unsolicited AEs, SAEs and pIMDs are only applicable for RSV_annual and RSV_flexible revaccination groups.

***For the RSV_annual group, the same ~345 participants will be part of both the HI and CMI subsets. The remaining ~645 participants will have no blood draws and will only be followed up for safety and reactogenicity.

****For those participants in the RSV_annual group without blood sample collections, visits at Months 6, 18, 30 and 36 may be held through a contact. However, contact should be attempted only if site visit is not possible at Months 6, 18, 30 and 36.

- Type of study: self-contained.
- **Experimental design**: Phase 3, randomized, open-label, multi-country study with 3 parallel groups (see Figure 1).
- **Duration of the study**: ~ 36 months for each participant.
- **Primary completion date**: Month 12.

- **Control**: none.
- **Blinding**: open-label. Refer to the protocol for details.
- **Data collection**: standardized electronic Case Report Form (eCRF). Solicited events and unsolicited adverse events (AEs) will be collected using a participant Diary card (paper Diary card).
- **Safety monitoring**: the study will be conducted with oversight by the project Safety Review Team (SRT). Please refer to protocol for the description of review of safety data by the SRT.
- **Study groups**: refer to Figure 1 and Table 1 for an overview of the study groups

Table 1Study groups, intervention and blinding foreseen in the study

				Intervention		Blinding
Study Groups	Number of participants	Age	Primary vaccination	Revaccination Year 1 (Month 12)	Revaccination Year 2 (Month 24)	Open
RSV_annual*	~990	≥60 years	RSVPreF3 OA investigational vaccine	RSVPreF3 OA investigational vaccine	RSVPreF3 OA investigational vaccine	х
RSV_flexible revaccination	~330	≥60 years	RSVPreF3 OA investigational vaccine	(none)	RSVPreF3 OA investigational vaccine	х
RSV_1dose	~330	≥60 years	RSVPreF3 OA investigational vaccine	(none)	(none)	х

* RSV_annual group will be split in 3 technical groups in SBIR in order to have a randomization ratio of 1:1:1:1:1: for treatment allocation and avoid predictability.

• **Groups and sub-groups definition for analysis:** Refer to the tables below for a description of the groups and subgroups labels that will be used in the Tables Figures and Listings (TFLs).

The analyses pertaining to timepoints up to Month 12 will be performed for each group and for the 3 groups pooled. From Month 13 up to study end, the analyses will be performed by group.

The following group names will be used in the TFLs:

Table 2 Group names and definition for footnote in the TFLs

Group order in tables	Group label in tables	Group definition for footnote	
1	RSV_annual	Participants receiving the first dose (Dose 1) of RSVPreF3 OA investigational vaccine at Day 1, followed by a revaccination dose at 12 months post-Dose 1 and at 24 months post-Dose 1	
2	RSV_flexible revaccination	Participants receiving the first dose (Dose 1) of RSVPreF3 OA investigational vaccine at Day 1 and a revaccination dose at 24 months post-Dose 1	
3	RSV_1dose	Participants receiving a single dose (Dose 1) of RSVPreF3 OA investigational vaccine at Day 1	

Pooled Group label in tables	Groups to be pooled	Pooled definition for footnote	Comment
Total	RSV_annual, RSV_flexible revaccination and RSV_1dose	Participants receiving one dose of RSVPreF3 OA investigational vaccine at Day 1 in all the three groups	Applicable on data reported up to Month 12
Flexible+1dose	RSV_flexible revaccination, and RSV_1dose	Participants receiving one dose of RSVPreF3 OA investigational vaccine at Day 1 in the RSV_flexible revaccination, and RSV_1dose groups	Applicable on data reported at Month 13, Month 18 and Month 24

Table 3Pooled group names and definition for footnote in the TFLs

Table 4Sub-group names and definitions for footnote in the TFLs

Sub-analysis	Subgroup order in tables	Subgroup label in tables	Subgroup definition for footnote
By age	1	≥65YOA	≥65 years old participants
	2	≥70YOA	≥70 years old participants
	3	≥80YOA	≥80 years old participants
	4	60-69YOA	60-69 years old participants
	5	70-79YOA	70-79 years old participants
By sex	1	Female	Female
	2	Male	Male
By region	1	North America	Participants from North America (United States of America)
	2	Europe	Participants from Europe (Finland, Germany)
	3	Asia	Participants from Asia (Japan, Taiwan)

YOA = Years of age

• Allocation of participants to assay subsets

Allocation of participants to assay subsets will be performed using SBIR. The subsets are detailed below.

	RSV_annual	RSV_flexible revaccination	RSV_1dose
HI subset	~345*	All participants (~330)	All participants (~330)
CMI subset	~345*	~115	~115

*For the RSV_annual group, the same ~345 participants will be part of both the HI and CMI subsets. The remaining ~645 participants will have no blood draws, and will only be followed up for safety and reactogenicity.

- **HI subset:** ~345 participants from the RSV_annual group, and all participants from the RSV_flexible revaccination and RSV_1dose groups. These participants will have blood samples collected for testing of humoral immunity at each visit applicable for their study group.
- **CMI subset**: ~345 participants from the RSV_annual group, and ~115 participants each from the RSV_flexible revaccination and RSV_1dose groups. These participants will have additional blood samples collected for CMI testing at each visit applicable for their study group.

4. ANALYSIS SETS

4.1. Definition

Table 5Populations for analyses

Analysis set	Description
Enrolled set	Participants who agreed to participate in a clinical study after completion of the informed consent process.
Exposed set (ES)	All participants who received at least 1 dose of the study intervention. The allocation in a group is done in function of the administered intervention.
Per Protocol set (PPS)	All participants who received at least 1 dose of the study intervention to which they are randomized and have post-vaccination data, minus participants with protocol deviations that lead to exclusion.

The primary analysis for immunogenicity will be performed on the Per Protocol set (PPS). If the percentage of vaccinated participants with serological results excluded from the PPS for immunogenicity is at least 5% for at least 1 visit and at least 1 group, a second analysis will be performed on the Exposed Set (ES). The immunogenicity analysis will be performed overall, by sex, by age category (age at Dose $1: \ge 65$ YOA, ≥ 70 YOA, ≥ 80 YOA, 60-69 YOA and 70-79 YOA, and by region (North America, Europe, Asia).

4.2. Criteria for eliminating data from Analysis Sets

4.2.1. Elimination from ES

Code 1030 (Study intervention not administered at all), 800 (Fraudulent data) and code 900 (Invalid informed consent) will be used for identifying participants eliminated from the ES.

4.2.2. Elimination from Per-protocol analysis Set (PPS)

4.2.2.1. Excluded participants

A participant will be excluded from the populations of analysis under the following conditions

- For codes 800, 900, 1030 and 1050: participants will be eliminated for all visits.
- For codes 1040, 1070, 1080, 1090, 2010, 2040, 2050, 2080: participants will be eliminated from a specific visit (at which the condition is met) onwards.
- For codes 2090, 2100h, 2100c, 2120: participants will be eliminated at the specific visit at which the condition is met.

Code	Condition under which the code is used	Visit (timepoints) where the code is checked	Applicable for analysis set
800	Fraudulent data	All	ES and PPS
900	Invalid informed consent	All	ES and PPS
1030	Study intervention not administered at all	All	ES and PPS
1040	Administration of concomitant vaccine(s) forbidden in the protocol	All	PPS
	 Any investigational or non-registered vaccine other than the study vaccine used during the study period beginning 30 days before the first dose of study vaccine, or planned use during the study period. Planned or actual administration of a vaccine not foreseen by the study protocol in the period starting 30 days before each dose and ending 30 days after each dose of study vaccine administration, with the exception of inactivated, split virion and subunit influenza vaccines which can be administered up to 14 days before or from 14 days after each study vaccination. 		
	 Previous vaccination with an RSV vaccine 		
1050	Randomization failure	Day 1	PPS
1070	Vaccine administration not according to protocolIncomplete vaccination course	Vaccination visits at Day 1, Month 12, and 24	PPS
	 Participant was vaccinated with the correct vaccine but containing a lower volume Participant was re-vaccinated 	Months 12 and 24 are applicable to the RSV_annual group and Month 24 applies	
	while it was not planned	to the RSV_flexible revaccination group	

Table 6List of elimination codes

Code	Condition under which the code is used	Visit (timepoints) where the code is checked	Applicable for analysis set
	 Route of the study intervention is not intramuscular Wrong reconstitution of administered vaccine 		
1080	 Vaccine administration after a Temperature deviation Vaccine administered despite a Good Manufacturing Practices (GMP) no-go temperature deviation 	Day 1, Month 12, and 24 Months 12 and 24 are applicable to the RSV_annual group and Month 24 applies to RSV_flexible revaccination group	PPS
1090	Vaccine administration after expiration	Day 1, Month 12, and 24 Months 12 and 24 are applicable to the RSV_annual group and Month 24 belongs to the RSV_flexible revaccination group	PPS
2010	Protocol deviation linked to inclusion/exclusion criteria	All	PPS
2040	 Administration of any medication forbidden by the protocol Any investigational or non- registered medication used during the study period Administration of long-acting immune-modifying drugs at 	All	PPS
	 any time during the study period (e.g. infliximab) Immunoglobulins and/or any 		
	 blood products administered during the study period Chronic administration (defined as more than 14 consecutive days in total) of immunosuppressants or other immune-modifying drugs during the period starting 		

Code	Condition under which the code is used	Visit (timepoints) where the code is checked	Applicable for analysis set
	90 days prior to the study vaccine administration or planned administration during the study period. For corticosteroids, this will mean prednisone ≥20 mg/day, or equivalent.		
2050	Intercurrent medical condition	All	PPS
	• Participants may be eliminated from the PPS for immunogenicity if, during the study, they incur a condition that has the capability of altering their immune response (intercurrent medical condition) or are confirmed to have an alteration of their initial immune status.		
2080	Participants did not comply with dosing schedule	Month 12 and 24	PPS
	• RSV_annual : number of days between dose 1 and revaccination dose at Month 12 is outside [350-380 days]		
	• RSV_annual and RSV_flexible revaccination: number of days between dose 1 and revaccination dose at Month 24 is outside [715-745 days]		
2090	Participants did not comply with blood sample schedule	Day 31, Month 6, 12, 13, 18, 24, 25, 30, 36	PPS
	• Number of days between dose 1 and Day 31 blood sample is outside [30-42 days]		
	• Number of days between dose 1 and Month 6 blood sample is outside [180-210 days]		
	• Number of days between dose 1 and Month 12 blood sample is outside [350-380 days]		

Code	Condition under which the code is used	Visit (timepoints) where the code is checked	Applicable for analysis set
	• Number of days between Month 12 and Month 18 blood sample is outside [180-210 days]		
	• Number of days between dose 1 and Month 24 blood sample is outside [715-745 days]		
	• Number of days between Month 24 and Month 30 blood sample is outside [180-210 days]		
	• Number of days between dose 1 and Month 36 blood sample is outside [1080-1110 days]		
	For RSV_annual group only:		
	• Number of days between revaccination at Month 12 and Month 13 blood sample is outside [30-42 days]		
	For RSV_annual and RSV_flexible groups:		
	• Number of days between revaccination at Month 24 and Month 25 blood sample is outside [30-42 days]		
2600*	Participants not included in the humoral immunogenicity subset	Day 1, 31, Month 6, 12, 13, 18, 24, 25, 30, 36	PPS
2700*	Participants not included in the cell-mediated immune response subset	Day 1, 31, Month 6, 12, 13, 18, 24, 25, 30, 36	PPS
2100h	 For participants in the humoral immunogenicity subset. No immunological result at visit x for all the following tests: RSV A/B Neutralizing antibody titer andRSVPreF3- specific IgG antibody concentration 	Day 1, Day 31, Month 6, 12, 13, 18, 24, 25, 30, 36 Month 13 and 25 are applicable to the RSV_annual and only Month 25 is applicable to the RSV_flexible revaccination group	PPS

Code	Condition under which the code is used	Visit (timepoints) where the code is checked	Applicable for analysis set
2100c	 For participants in the CMI subset No immunological result at visit x for all the following tests: Frequency of RSVPreF3-specific CD4+ and CD8+ T cells 	Day 1, Day 31, Month 6, 12, 13, 18, 24, 25, 30, 36 Month 13 and 25 are applicable to the RSV_annual and only Month 25 is applicable to the RSV_flexible revaccination group	PPS
2120	 Obvious incoherence or abnormality or error in laboratory data Unreliable released data as a result of confirmed sample mismatch or confirmed inappropriate sample handling at laboratory 	Day 1, 31, Month 6, 12, 13, 18, 24, 25, 30, 36	PPS

* codes 2600 and 2700 are not considered as protocol deviations, but those codes will be used to identify participants that are not part of the immunogenicity subsets.

5. STATISTICAL ANALYSES

Standard data derivation rules and stat methods are described in Section 10.1 while the study specific data derivation rules and stat methods are described in Section 9.

For the sake of analysis, data up to Month 12 will be analyzed by group (RSV_annual, RSV_flexible revaccination and RSV_1dose), and also the 3 groups will be pooled. For Month 13, Month 18 and Month 24, the analyses will be tabulated for RSV_annual group versus the pooled RSV_flexible revaccination and RSV_1dose groups. From Month 25 up to study end, the analyses will be performed by group

If more than 5% of participants in the RSV_annual and RSV_flexible revaccination groups receive different number of doses, an analysis by subgroup according to the number of dose(s) administered might be performed. The goal of this analysis is to describe the characteristics of participants in the RSV_annual and RSV_flexible revaccination groups who ultimately receive different numbers of revaccination doses in order to rule out the possibility of systematic differences between these subgroups.

5.1. General considerations

5.1.1. Demography

For a given participant and a given demographic variable, missing measurements will not be replaced.

5.1.2. Immunogenicity

- Any missing or non-evaluable immunogenicity measurement will not be replaced. The descriptive analysis performed for each assay at each timepoint will exclude participants with a missing or non-evaluable measurement. This is applicable to the standard way of computing geometric mean titers/concentrations (GMTs/GMCs).
- During the computation of GMTs/GMCs from the mixed effects model (Section 5.4.3.1). Multiple imputation (MI) technique will not be applied for any missing immunogenicity measurement. This is because the mixed effects model inherently accounts for the missingness, under the assumption that the missing data are missing at random (MAR). Thus considering that missing data are MAR is a reasonable assumption for this descriptive clinical trial, then it is not necessary to perform MI [Rubin et al., 1995]
- The GMTs/GMCs will be computed by taking the anti-logarithm of the arithmetic mean of the log₁₀ transformed titers/concentrations.
- A seronegative participant will be defined as a participant whose antibody titer/concentration is below the technical cut-off value of the assay. A seropositive participant is a participant whose antibody titer/concentration is greater than or equal to the technical cut-off value of the assay.
- Antibody titers/concentrations below the technical assay cut-off will be given an arbitrary value of half the technical assay cut-off for the purpose of GMT/GMC calculation.
- Antibody titers/concentrations above the Upper Limit of Quantification (ULOQ) value will be given the ULOQ value for the purpose of GMT/GMC calculation.
- The mean geometric increase (MGI) is calculated by the geometric mean of ratios of antibody titers/concentrations of each post vaccination time point over pre vaccination (Day 1).

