5.4. Secondary endpoint(s)

5.4.1. Humoral immune response

The same analyses as described above for the primary endpoint will be performed for RSVPreF3-specific IgG ELISA up to Month 12 and for each timepoint with blood sample collection for humoral immune response **from study Month 13 up to study end** and for each assay (RSVpreF3-specific IgG **ELISA and RSV-A/-B neutralization assays**). For Month 13, Month 18, and Month 24, the analyses will be tabulated for RSV_annual group versus the pooled RSV_flexible revaccination and RSV_1dose groups. From Month 25 up to study end, the analyses will be performed by group.

Only the analyses requiring further clarification of the exact timepoints analyzed are summarized below:

Within groups evaluation:

- The MGI i.e. geometric mean of ratios of antibody titer/concentrations will be tabulated with 95% CI:
 - For each post-primary vaccination time point (at Months 18, 24, 30 and 36 when applicable) over pre-primary vaccination (Day 1),
 - For each post-revaccination time point over corresponding pre-revaccination (Months 12 and 24) in the RSV_annual group,
 - For each post-revaccination timepoint over corresponding pre-revaccination (Month 24) in the RSV_flexible revaccination group,
 - For 1 month post-revaccination at Month 12 (Month 13) over 1 month post-Dose 1 vaccination (Day 31) in RSV_annual group.
 - For 1 month post-revaccination at Month 24 (Month 25) over 1 month post-revaccination at Month 12 (Month 13) in RSV_annual group
 - For 1 month post-revaccination at Month 24 (Month 25) over 1 month post-Dose 1 vaccination (Day 31) in RSV_flexible revaccination group.

In addition, the following evaluation will be performed:

• The kinetics of GMTs/GMCs will be plotted as a function of time for participants with results available at all post vaccination timepoints.

The immunogenicity analysis will be performed overall, by sex, age category (age at Dose $1: \ge 65$ YOA, ≥ 70 YOA, ≥ 80 YOA, 60-69 YOA and 70-79 YOA), and region (North America, Europe, Asia).

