10.1.3.3. Numerical serology results

Numerical serology results will be derived from the content of IS.ISORRES in the SDTM dataset. For humoral assays with a specific cut-off, the following derivation rules apply:

IS.ISORRES	Derived value
"NEG", "-", or "(-)"	cut-off/2
"POS", "+", or "(+)"	cut-off
"< value" and value is <= assay cut-off	cut-off/2
"< value" and value is > assay cut-off	Value
"> value" and value is < assay cut-off	cut-off/2
"> value" and value is >= assay cut-off	Value
"value" and value is < cut-off	cut-off/2
"value" and value is >= cut-off and value is <=ULOQ	value
"value" and value is > ULOQ	ULOQ*
All other cases	Missing

*This rule will be used to compute descriptive statistics (GMTs, fold increase etc).

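### Results above ULOQ are cut to ULOQ, and '<value' results above the cut-off are counted as seropositive, with no count of either and no censored-data check

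*SAP*

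**What the plan says.** SAP Amendment 3 handles out-of-range antibody results in 5.1.2 and in the table of 10.1.3.3.

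- **Above ULOQ.** "Antibody titers/concentrations above the Upper Limit of Quantification (ULOQ) value will be given the ULOQ value for the purpose of GMT/GMC calculation". In 10.1.3.3 the rule applies to a numeric result above ULOQ, and the footnote gives its scope: "This rule will be used to compute descriptive statistics (GMTs, fold increase etc".
- **Below the cut-off.** "Antibody titers/concentrations below the technical assay cut-off will be given an arbitrary value of half the technical assay cut-off for the purpose of GMT/GMC calculation".
- **Reported only as an upper bound that exceeds the cut-off.** The row headed "< value' and value is > assay cut-off" assigns the bound itself.
- **Seropositivity.** "A seropositive participant is a participant whose antibody titer/concentration is greater than or equal to the technical cut-off value of the assay".

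The estimates exposed to these rules are the GMTs at each visit, the MGI, and the ratios listed in 5.4.1. On the MGI, 5.1.2 says: "The mean geometric increase (MGI) is calculated by the geometric mean of ratios of antibody titers/concentrations of each post vaccination time point over pre vaccination", with Day 1 as the reference. Section 5.4.1 adds ratios over pre-revaccination and three peak-over-peak ratios. One is "For 1 month post-revaccination at Month 12 (Month 13) over 1 month post-Dose 1 vaccination (Day 31) in RSV_annual group"; the others are Month 25 over Month 13 (RSV_annual) and Month 25 over Day 31 (RSV_flexible revaccination).

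Neither document states a ULOQ or a cut-off; SAP 10.1.3.4 says only that the laboratory defines cut-offs before the analysis. No table of out-of-range results is planned. The immunogenicity sensitivity analyses in SAP 5.4.3.4 concern participants with full follow-up, not these rules.

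**The concern.** A result above ULOQ is right-censored, and cutting it to ULOQ biases the mean log titre downwards. The bias is largest where titres are highest. Protocol 4.3 reports that in the earlier dose-selection study the response peaked one month after Dose 1, so here the visits most exposed are Day 31 and the post-revaccination visits, Months 13 and 25. Day 31 is a primary-endpoint visit. How fast the response declines from its peak, and whether a later dose restores that peak, are what the trial sets out to describe. Both depend on peak values.

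A '<value' result with value above the cut-off is left-censored. The true titre may lie on either side of the cut-off. The SAP enters it at the highest titre consistent with the report and so classes it as seropositive. That is a fault of logic at any frequency. Within the same table, a left-censored result gets half the cut-off in one row and the full bound in another.

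As planned, a reader of the results could not tell how many values were altered or whether it mattered.

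**Working it through.** **Inputs from the documents.** SD of log10 titre 0.30-0.50 and n = 804 (Protocol Table 17), and the SAP rules above. **Assumptions.** Log10 titres are normal, with equal SD and the same ULOQ at the visits compared. The shares out of range, the decay rate and the true ratios are illustrative, because the documents give none.

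**1. The plan's own figure.** Table 17 half-width = t(0.975, 803) × SD/√804. SD 0.30, 0.40 and 0.50 give 0.0208, 0.0277 and 0.0346; the protocol states 0.021, 0.028 and 0.035. Reproduced.

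**2. Peak GMT.** With share p above ULOQ and z = Φ⁻¹(1−p), the downward shift in mean log10 is SD × [φ(z) − z·p]. For p = 10%: z = 1.2816 and φ(z) = 0.1755, so the bracket is 0.0473. SD 0.30 gives 0.0142 and SD 0.50 gives 0.0237. The GMT is then low by 1 − 10^(−shift).

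| Share above ULOQ | SD 0.30 | SD 0.40 | SD 0.50 |
|---|---|---|---|
| 1% | 0.2% | 0.3% | 0.4% |
| 5% | 1.4% | 1.9% | 2.4% |
| 10% | 3.2% | 4.3% | 5.3% |
| 20% | 7.4% | 9.8% | 12.1% |

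The shift equals the Table 17 half-width at about 13.7% above ULOQ, whatever the SD, since both scale with it. Table 17 refers to Month 12, so it serves here only as a yardstick.

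**3. Ratios to a peak.** The bias of a ratio is the Day 31 shift minus the shift at the other visit.
- Later visit truly 0.2-0.4 log10 lower, SD 0.30-0.50: the ratio to Day 31 is too high by a factor of 1.012-1.022 (5% of Day 31 results above ULOQ), 1.026-1.048 (10%) or 1.059-1.110 (20%).
- Month 13 over Day 31, SD 0.40: a true 0.70 reads 0.718 (10%) or 0.739 (20%); a true 1.20 reads 1.174 or 1.151. The pull is towards 1 from either side.

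**4. Decline and late level.** Assume a power law with true decay 0.40, SD 0.40, and that the persistence models use the same cut values, which the SAP does not state. At 5%, 10% and 20% above ULOQ the fitted decay is 0.395, 0.388 and 0.372. Month 12 over Day 31 reads 0.377, 0.386 and 0.406 against a true 0.370. The extrapolated Month 60 level, relative to the true Day 31 level, is 0.195-0.199 against a true 0.194, so the absolute late level hardly moves.

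**5. MGI over Day 1 at the peak.** Assumed true rise 10^0.9 = 7.94-fold, SD 0.40. With 10% of peak results cut, 10^(0.9 − 0.0189) = 7.60. If 10% of Day 1 results are also '<value' entered at value, 10^(0.9 − 0.0189 − 0.0189) = 7.28. The increase is understated.

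**6. '<value' results.** If a share f of sera truly lie 4-fold below the value entered, the GMT is too high by 4^f: 4^0.01 = 1.014 and 4^0.03 = 1.042. All of them count as seropositive.

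**7. Below the cut-off.** With the mean set to 0 and the cut-off at L (log10), the half-cut-off shift is p(L − log10 2) + SD·φ(L/SD), where p is the share below the cut-off. At SD 0.40 this is −1.5% on the GMT for p = 5% and −3.5% for 20%. Over SD 0.30-0.50 and p = 1-30% it runs from −7.4% to +1.1%, so this rule mostly lowers the GMT.

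**The case against.** The case for leaving the SAP alone is substantial. The study is descriptive (Protocol 9.1), and the ULOQ and half-cut-off rules are pre-specified in both documents. Reverse cumulative curves (SAP 5.3.1.1) would show a pile-up at ULOQ if the cut values are plotted. Every magnitude above rests on an assumed share. All of that stands, and it keeps this a minor point. The curves do not count or correct anything, however, and they do not touch the seropositivity fault.

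Some stronger readings are not supported:

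- **That every out-of-range result is fixed at a bound, so low values are raised in general.** Results below the cut-off get half the cut-off, which mostly lowers the GMT (step 7). Only '<value' results above the cut-off are raised.
- **That the trial will overstate persistence.** This holds only relative to the Day 31 peak. The later persistence measure listed in 5.4.1 is the MGI over Day 1, and cutting at ULOQ scarcely affects it at late visits. At the peaks, MGIs over Day 1 or over pre-revaccination are understated. No late-over-Day 31 ratio is among the listed MGIs; that decline enters through GMT profiles and the exploratory models of 5.4.3.3.
- **That a table row for values above ULOQ shows they are expected.** Section 10.1 holds standard rules for studies in general, and the same table has rows for purely qualitative results. A row says nothing about frequency.
- **That the '<value' row contradicts 5.1.2**, which says: "Any missing or non-evaluable immunogenicity measurement will not be replaced". A '<value' report is a bounded result, not a missing or non-evaluable one, and 5.1.2 itself assigns values to other out-of-range results.

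**Conclusion.** The concern holds in limited form. Cutting at ULOQ lowers the peak GMTs and, if a material share is affected, draws peak-over-peak ratios and the decline from Day 31 towards 1. It understates the MGI over Day 1 at the peaks and leaves absolute late GMTs almost unchanged. Separately, the '<value' row classes sera of undetermined status as seropositive; that conclusion needs no assumption about frequency.

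The size is unknown. Under log-normal titres and the planned SDs, the effect on the Day 31 GMT is negligible at 1% above ULOQ and comparable with the planned Month 12 precision only near 14%. No reported result is shown to be wrong. What is missing is the count that would show whether the rules matter, and an analysis to fall back on if they do.

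**What to change.** In SAP 5.1.2 and 10.1.3.3:

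1. Tabulate, by assay, group and visit, the number and percentage of results above ULOQ and of '<value' results with value above the cut-off.
2. Where either exceeds a pre-stated share (for example 1%) at a visit used in a ratio, add a sensitivity analysis of GMTs and MGIs from a censored-normal likelihood on log10 titres, right-censored at ULOQ and left-censored at value. Keep the current rule as the main analysis. PROC NLMIXED is already used in 5.4.3.3.
3. Stop counting '<value' above the cut-off as seropositive. Treat it as indeterminate for the seropositivity percentage and as left-censored in the sensitivity GMT.

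These results should not be set to missing for GMTs, because dropping low censored values can do more harm than the present rule. Illustration: 3% of sera, value 0.8 log10 below the mean of the rest, true titre 4-fold (0.602 log10) lower. The true contribution is 0.03 × (−0.8 − 0.602) = −0.0421. The current rule enters 0.03 × (−0.8) = −0.0240, an error of 0.0181 log10 or +4.2%. Dropping them gives an error of 0.0421 log10, about +10%.

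The cost is SAP wording, one extra table, and a conditional run that assumes log-normal titres. A few results leave the seropositivity denominator. No new samples or retesting are needed.
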